11.0 DATA AND SAFETY MONITORING AND QUALITY ASSURANCE

This study will be monitored regularly by the Data Review Committee (DRC) of the Dan L Duncan Comprehensive Cancer Center, at a frequency of at least once per year, in accordance with the

DLDCCC Data and Safety Monitoring Plan. The DRC will monitor the study for progress and enrollment, toxicities, adverse events, and soundness of data.

This study will be monitored by the DLDCCC Quality Assurance program for study conduct and quality of data.

12.0 DATA MANAGEMENT

The patient eligibility data, initial history and physical examination will be recorded on the protocol chart. A record of relevant outpatient visits and hospital admissions will be recorded in the patient's clinic chart.

All trial data will be recorded in OnCore.

For patients going off-study, a final assessment summary will be recorded by the investigator in the protocol chart indicating clearly the reasons for discontinuing protocol treatment.

13.0 ADVERSE EVENT REPORTING

13.1 Adverse Event: Any unfavorable medical occurrence in a human subject, including any abnormal sign, symptom, or disease, whether or not it is considered related to the subject's participation in the research.

13.2 Descriptions and Grading: the descriptions and grading scales found in the NCI Common Terminology Criteria for Adverse Events (CTCAE) version 4.0 will be utilized for all toxicity reporting. A copy of the CTCAE version 4.0 can be downloaded from the CTEP website.

13.3 Attribution / Relatedness: Each event should be evaluated for its relatedness to participation in the research:

- Definite: The AE *is clearly related* to the study treatment.
- Probable: The AE *is likely related* to the study treatment.
- Possible: The AE *may be related* to the study treatment.
- Unlikely: The AE *is doubtfully related* to the study treatment.
- Unrelated: The AE *is clearly NOT related* to the study treatment.

13.4 Seriousness: A Serious Adverse Event (SAE) is any adverse event that:

- Results in death;
- Is life-threatening;
- Results in inpatient hospitalization or prolongation of existing hospitalization;
- Results in a persistent or significant disability/incapacity;
- Results in a congenital anomaly/birth defect; or
- Based upon appropriate medical judgment, may jeopardize the subject's health and may require medical or surgical intervention to prevent one of the other outcomes listed in this definition

13.5 Expectedness: Definition of expected and unexpected adverse event.

13.5.1 Expected adverse events are those that have been previously identified as resulting from administration of the agent. For purposes of this study, an adverse event is considered expected when it appears in the current adverse event list in the Investigator's Brochure, the package insert, or is included in the informed consent document as a potential risk.

13.5.2 An adverse event is considered unexpected when it varies in nature, intensity, or frequency from information provided in the current adverse event list in the Investigator's Brochure, the package insert or when it is not included in the informed consent document as a potential risk.

13.6 Reporting:

13.6.1 Adverse events will be collected and reporting beginning on the first day of post-operative chemotherapy treatment, and continuing through completion of post-operative treatment.

13.6.2 All adverse events, grade 3 or above, regardless of relatedness, will be reported and recorded on the appropriate CRFs. Toxicities that were present at baseline (pre-treatment) should not be reported unless the toxicity worsens.

13.6.3 New AEs and SAEs that are ongoing at the end of postoperative chemotherapy will be followed for 2 weeks from the patient's receipt of the last dose of protocol therapy, unless they have resolved earlier. SAEs and drug related AEs ongoing at the end of treatment will be followed until resolution.

13.6.4 The AE description will include the nature of the experience, the date of onset, the resolution date, the severity of each sign or symptom reported using the NCI-CTCAE (v 4.0), the seriousness of the event, the relatedness to study treatment, the course of action taken (if any), and the outcome of the experience.

13.6.5 SAEs are to be reported to the institutional review board (IRB) according to the IRB's reporting requirements and required time frame.

13.6.6 Any event that is reportable to the BCM IRB must also be reported to the DLDCCC Data Review Committee (DRC) via the Patient Safety Officer at [contact].

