6.4.1.5 Survival Status

6.4.1.6 Recurrence of disease (date of recurrence)

6.4.1.7 Adverse Event Assessment (per Section 13.6.3)

6.4.2 Patients will undergo imaging for residual or recurring tumor with either CT (chest with contrast and abdomen/pelvis with and without contrast) or CT/PET (skull base to mid-thigh). The interval of this imaging can be every 3-6 months, at the discretion of the treating investigator.

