15.0 APPENDIX I: SCHEDULE AND FLOW OF EVALUATIONS

15.1 ARM 1: Node-Negative, Adjuvant Chemotherapy.

Study Procedures	Screening & Baseline (1)	Arm 1: Cycle 1 (6)	Arm 1: Cycle 2 (6)	Arm 1: Cycle 3 (6)	Post-Treatment Surveillance, every 3 months (7)
Informed Consent	X				
History & Physical Exam; Vitals (2); ECOG PS	X	X	X	X	X
CBC + differential + platelets	X	X	X	X	X
CMP: Serum Chemistries (3)	X	X	X	X	X
AE Assessment		X	X	X	X
Pregnancy Test	X				
Tumor for genetic profile (4)	X				
Imaging (5)	X				X
Chemo, Adjuvant		X	X	X	
Survival Status, Recurrence					X

1. Screening procedures must be obtained within 28 days registration, with the exception of radiographic studies and tumor samples for baseline profiles.
2. Vital signs includes blood pressure, respiratory rate, height, and weight.
3. Serum chemistries to include: liver enzymes (AST, ALT, alkaline phosphatase), blood urea nitrogen (BUN), creatinine, electrolytes (sodium, potassium, chloride, calcium, bicarbonate), total protein, albumin, total bilirubin, glucose.
4. Tumor samples from diagnostic biopsy (before neo-adjuvant chemo) and surgery (after neo-adjuvant chemo) should be obtained (after subject consents to participate).
5. Can be either (1) CT of the chest with contrast and CT of the abdomen/pelvis with and without contrast, or (2) PET/CT from the skull base to mid-thigh. Baseline imaging must be after surgery, and within 42 days of starting adjuvant chemotherapy.
6. Procedures are to be repeated at the beginning of each cycle and can be assessed up to 2 days in advance of D1 for each cycle. These cycles are 14 days long if FOLFOX used and 21 days long if CAPEOX used.
7. Three month interval begins from the end of completion of chemotherapy, and continues until 36 months after surgery (unless patient comes off study, per Section 6). These assessments can be +/- 14 days from planned date. Imaging assessments during follow-up can occur every 3-6 months, per investigator's standard practice. If subject has disease recurrence, follow-up will stop.

15.2 ARM 2: Node-Positive, Adjuvant Chemoradiation.

Study Procedures	Screening & Baseline (1)	Arm 2: Chemo alone, Cycle 1 28-day cycle (6)	Arm 2: ChemoRT, 5 weeks Schedule is for each week					Arm 2: Chemo alone, Cycle 2 28-day cycle (6)	Arm 2: Chemo alone, Cycle 3 28-day cycle (6)	Post-Treatment Surveillance, every 3 months (7)
			W 1	W 2	W 3	W 4	W 5			
Informed Consent	X									
History & Physical Exam; Vitals (2); ECOG PS	X	X	X	X	X	X	X	X	X	

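### A treatment-related grade 3+ AE or SAE that starts after post-operative treatment ends need not be entered on a CRF, even when it is found at a surveillance visit

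*Combined protocol and SAP*

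**What the plan says.** Five places in the combined protocol and SAP bear on this.

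- **13.6.1** gives the only collection window in Section 13: "Adverse events will be collected and reporting beginning on the first day of post-operative chemotherapy treatment, and continuing through completion of post-operative treatment". It has no tail after treatment.
- **13.6.2** says what goes on a form: "All adverse events, grade 3 or above, regardless of relatedness, will be reported and recorded on the appropriate CRFs". It states no time limit.
- **13.6.3** covers the period after treatment. Its first sentence begins "New AEs and SAEs that are ongoing at the end of postoperative chemotherapy will be followed for 2 weeks", counted from the last dose. Its second reads "SAEs and drug related AEs ongoing at the end of treatment will be followed until resolution".
- **6.4.1.7** lists the AE item at each three-monthly surveillance visit as "Adverse Event Assessment (per Section 13.6.3" and cites no other section.
- **Appendix I, 15.1 (Arm 1 schedule)** marks AE assessment in the surveillance column. Footnote 7 gives only the timing: "Three month interval begins from the end of completion of chemotherapy, and continues until 36 months after surgery". The Arm 2 schedule is misaligned in the extracted text and is not used here.

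Separately, 13.6.5 sends SAEs to the IRB under the IRB's own rules, and 13.6.6 sends IRB-reportable events on to the Data Review Committee (DRC). Neither states a cut-off date.

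**The concern.** Section 3.2 calls chemoradiation after preoperative chemotherapy and surgery experimental. It makes feasibility depend on whether patients can tolerate the therapy, and says this must be settled before a larger study is considered. Toxicity that appears after the last cycle would help in planning that study.

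The surveillance visits that could detect it already exist, with history, examination, laboratory tests and an AE assessment. As written, an investigator could find a new treatment-related grade 3 event at such a visit, follow the protocol exactly, and leave it out of the trial's AE data. The post-treatment toxicity summary would then consist of events that began on treatment, and could understate late toxicity by an amount that cannot be recovered from the CRFs.

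**Working it through.** **Step 1: trace one event through the text.** Take a non-serious grade 3 event, judged probably related to radiation, that starts five months after the last cycle and is found at a surveillance visit.

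| Section | Does it require a CRF entry? |
|---|---|
| 13.6.1 | No. Collection has ended. |
| 13.6.2 | Only if read without the 13.6.1 window. |
| 13.6.3 | No. The event was not ongoing when treatment ended. |
| 6.4.1.7 | No. Its scope is that of 13.6.3. |
| 13.6.5 | No. It concerns SAEs and the IRB. |
| 13.6.6 | No. It applies only to IRB-reportable events, and concerns the DRC. |

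If the event were serious, 13.6.5 and possibly 13.6.6 would apply, but neither is a CRF rule. The result turns on 13.6.2. Letting 13.6.1 govern it is an inference, but the more natural one: if 13.6.2 had no time limit, 13.6.1 would have little left to do.

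**Step 2: length of the period.** The plan states no figure to reproduce. Inputs:

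- Surveillance runs to 36 months after surgery (6.4.1), every 3 months.
- Treatment starts 0 to 90 days after surgery (5.1, criterion 4). Day 0 is only the arithmetic limit.
- Arm 2 course (7.2 and 7.2.1): 28 + 35 + 2 × 28 = 119 days.
- Arm 1 course (15.1, footnote 6): 3 × 14 = 42 days (FOLFOX) or 3 × 21 = 63 days (CAPEOX).
- One month = 365.25/12 = 30.4375 days (my convention).

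Months remaining = 36 − (start day + course days)/30.4375. Visits = whole number of 3-month intervals in that time, counted from the end of the last cycle.

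| Arm | Start day | Calculation | Months | Visits |
|---|---|---|---|---|
| Arm 2 | 0 | 36 − 119/30.4375 | 32.1 | 10 |
| Arm 2 | 90 | 36 − 209/30.4375 | 29.1 | 9 |
| Arm 1 FOLFOX | 0 | 36 − 42/30.4375 | 34.6 | 11 |
| Arm 1 FOLFOX | 90 | 36 − 132/30.4375 | 31.7 | 10 |
| Arm 1 CAPEOX | 0 | 36 − 63/30.4375 | 33.9 | 11 |
| Arm 1 CAPEOX | 90 | 36 − 153/30.4375 | 31.0 | 10 |

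**Step 3: what shortens it.** Section 8 allows follow-up to stop at recurrence. In Arm 2, recurrence at 24 months leaves 24 − 3.9 = 20.1 to 24 − 6.9 = 17.1 months (6 to 5 visits). Recurrence at 12 months leaves 8.1 to 5.1 months (2 to 1 visits). Treatment delays shorten the period by their own length.

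**Step 4: a generous reading of 13.6.3.** Suppose its first sentence also covered events that start within two weeks of the last dose. Fourteen days is 14/30.4375 = 0.46 months, which is 0.46/32.1 = 1.4% to 0.46/29.1 = 1.6% of the Arm 2 period. The gap would be almost unchanged.

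**The case against.** The strongest counter-arguments, and what stands of each:

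- **13.6.2 has no window, so late grade 3 events already belong on a CRF.** The text permits this reading, and the point depends on rejecting it. It does not settle the matter, because 6.4.1.7 directs the surveillance assessment to 13.6.3 and not to 13.6.2.
- **Late events are captured elsewhere.** This stands in part. SAEs may reach the IRB and DRC, deaths appear under survival status, and Section 12 has relevant outpatient visits and hospital admissions recorded in the clinic chart. A reader might infer that late SAEs go unreported altogether; the documents do not support that. But none of these routes requires CRF entry, and none is an explicit reporting route for a late non-serious grade 3 event.
- **On-treatment toxicity is followed.** This stands. SAEs and drug-related AEs still ongoing at the end of treatment are followed to resolution. The gap concerns new onset only.
- **The endpoint is completion of therapy.** This stands. An event after the last cycle cannot change whether therapy was completed, and the plan has no safety endpoint. Section 3.2 also describes the individual components as established standards. The case for change is information for the next study.
- **The Arm 1 schedule does not contradict the text.** This stands. A reader might infer that it sets a wider AE scope than 6.4.1.7. It sets no scope: it has a mark without the cross-reference, and 6.4.1.7 supplies the limit.

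A reader might also expect sites to record late events differently. The documents name one IRB and one cancer center, so they give no basis for a between-site argument.

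**Conclusion.** The point holds as a low-cost improvement of low to moderate importance. Under the reading that 13.6.1 governs 13.6.2, nothing requires a CRF entry for a treatment-related grade 3+ AE or SAE that starts after post-operative treatment. In Arm 2 this applies to about 29 to 32 months of planned follow-up, assuming the full course without delay, a start within 90 days of surgery, and no recurrence.

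Those months measure time without required recording. They do not measure harm or lost events: the documents give no late-event rate, so no number of missed events can be stated. Sample size, interval width and the feasibility decision are untouched.

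Two smaller wording gaps belong with it. Section 13.6.1 names only completion, while Section 8 keeps patients who stop early for toxicity or delay in follow-up. The toxicity that made them stop began on treatment and is covered, so what is missing is an explicit end of collection for them. Within 13.6.3, an SAE ongoing at the end of treatment falls under both the two-week rule and the until-resolution rule.

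**What to change.** 1. **13.6.1:** collect AEs from the first day of post-operative treatment through its completion or discontinuation. Thereafter, at each scheduled surveillance visit until the subject comes off study, record any new grade 3 or higher AE, or any new SAE, judged possibly, probably or definitely related to chemotherapy or radiation.
2. **13.6.3:** keep it for events already ongoing, and state that the two-week limit applies only to those that are both non-serious and unrelated.
3. **Cross-references:** point 6.4.1.7, and the AE assessment row in both Appendix I schedules, to 13.6.1 as well as 13.6.3.
4. **Section 10:** report these events descriptively by arm, separating onset on treatment from onset afterwards. No test or interval is needed.

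The cost is a wording amendment and occasional CRF entries at visits that already take place; no visit or test is added. The split by onset needs no new data item, since 13.6.4 already specifies "The AE description will include the nature of the experience, the date of onset, the resolution date" and relatedness. The downside is a small data-entry burden and uncertain attribution late in follow-up or near recurrence. Limiting late collection to related grade 3+ AEs and SAEs keeps that burden small.

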15.0 APPENDIX I: SCHEDULE AND FLOW OF EVALUATIONS

15.1 ARM 1: Node-Negative, Adjuvant Chemotherapy.

Study Procedures	Screening & Baseline (1)	Arm 1: Cycle 1 (6)	Arm 1: Cycle 2 (6)	Arm 1: Cycle 3 (6)	Post-Treatment Surveillance, every 3 months (7)
Informed Consent	X				
History & Physical Exam; Vitals (2); ECOG PS	X	X	X	X	X
CBC + differential + platelets	X	X	X	X	X
CMP: Serum Chemistries (3)	X	X	X	X	X
AE Assessment		X	X	X	X
Pregnancy Test	X				
Tumor for genetic profile (4)	X				
Imaging (5)	X				X
Chemo, Adjuvant		X	X	X	
Survival Status, Recurrence					X

1. Screening procedures must be obtained within 28 days registration, with the exception of radiographic studies and tumor samples for baseline profiles.
2. Vital signs includes blood pressure, respiratory rate, height, and weight.
3. Serum chemistries to include: liver enzymes (AST, ALT, alkaline phosphatase), blood urea nitrogen (BUN), creatinine, electrolytes (sodium, potassium, chloride, calcium, bicarbonate), total protein, albumin, total bilirubin, glucose.
4. Tumor samples from diagnostic biopsy (before neo-adjuvant chemo) and surgery (after neo-adjuvant chemo) should be obtained (after subject consents to participate).
5. Can be either (1) CT of the chest with contrast and CT of the abdomen/pelvis with and without contrast, or (2) PET/CT from the skull base to mid-thigh. Baseline imaging must be after surgery, and within 42 days of starting adjuvant chemotherapy.
6. Procedures are to be repeated at the beginning of each cycle and can be assessed up to 2 days in advance of D1 for each cycle. These cycles are 14 days long if FOLFOX used and 21 days long if CAPEOX used.
7. Three month interval begins from the end of completion of chemotherapy, and continues until 36 months after surgery (unless patient comes off study, per Section 6). These assessments can be +/- 14 days from planned date. Imaging assessments during follow-up can occur every 3-6 months, per investigator's standard practice. If subject has disease recurrence, follow-up will stop.

15.2 ARM 2: Node-Positive, Adjuvant Chemoradiation.

Study Procedures	Screening & Baseline (1)	Arm 2: Chemo alone, Cycle 1 28-day cycle (6)	Arm 2: ChemoRT, 5 weeks Schedule is for each week					Arm 2: Chemo alone, Cycle 2 28-day cycle (6)	Arm 2: Chemo alone, Cycle 3 28-day cycle (6)	Post-Treatment Surveillance, every 3 months (7)
			W 1	W 2	W 3	W 4	W 5			
Informed Consent	X									
History & Physical Exam; Vitals (2); ECOG PS	X	X	X	X	X	X	X	X	X	
CBC + differential + platelets	X	X	X	X	X	X	X	X	X	
CMP: Serum Chemistries (3)	X	X	X	X	X	X	X	X	X	
AE Assessment		X	X	X	X	X	X	X	X	
Pregnancy Test	X									
Tumor for genetic profile (4)	X									
Imaging (5)	X								X	
Chemo, Adjuvant		X	X	X	X	X	X	X	X	
Concurrent XRT			X	X	X	X	X			
XRT Treatment Report (8)							X			
Survival Status, Recurrence									X	

1. Screening procedures must be obtained within 28 days of registration, with the exception of radiographic studies and tumor samples for baseline profiles.
2. Vital signs includes blood pressure, respiratory rate, height, and weight.
3. Serum chemistries to include: liver enzymes (AST, ALT, alkaline phosphatase), blood urea nitrogen (BUN), creatinine, electrolytes (sodium, potassium, chloride, calcium, bicarbonate), total protein, albumin, total bilirubin, glucose.
4. Tumor samples from diagnostic biopsy (before neo-adjuvant chemo) and surgery (after neo-adjuvant chemo) should be obtained (after subject consents to participate).
5. Can be either (1) CT of the chest with contrast and CT of the abdomen/pelvis with and without contrast, or (2) PET/CT from the skull base to mid-thigh. Baseline imaging must be after surgery, and within 42 days of starting adjuvant chemotherapy.

6. Procedures are to be repeated at the beginning of each cycle and can be assessed up to 2 days in advance of D1 for each cycle.
7. Three month interval begins from the end of completion of chemotherapy, and continues until 36 months after surgery (unless patient comes off study, per Section 6). These assessments can be +/- 14 days from planned date. Imaging assessments during follow-up can occur every 3-6 months, per investigator's standard practice. If subject has disease recurrence, follow-up will stop.
8. XRT treatment is reported once, at the completion of chemoXRT.

16.0 APPENDIX II: ECOG PERFORMANCE STATUS SCALE

ECOG PERFORMANCE STATUS *	
Grade	ECOG
0	Fully active, able to carry on all pre-disease performance without restriction
1	Restricted in physically strenuous activity but ambulatory and able to carry out work of a light or sedentary nature, e.g., light house work, office work
2	Ambulatory and capable of all self-care but unable to carry out any work activities. Up and about more than 50% of waking hours
3	Capable of only limited self-care, confined to bed or chair more than 50% of waking hours
4	Completely disabled. Cannot carry on any self-care. Totally confined to bed or chair
5	Dead

* As published in Am. J. Clin. Oncol.: Oken, M.M., Creech, R.H., Tormey, D.C., Horton, J., Davis, T.E., McFadden, E.T., Carbone, P.P.: *Toxicity And Response*
